## **5.4 Secondary Analyses of Objective 2 Primary Effectiveness Outcome Measure within the Primary Objective 2 Sample**

### **5.4.1 Objective 2 Covariate-adjusted Model**

We will apply a sensitivity analysis that includes additional covariate adjustment beyond the number of days of acute care at baseline. We plan to additionally adjust for the following pre-specified covariates, identified based on known and hypothesized predictors of acute care utilization among patients with OUDs identified from the literature and from discussions with study co-investigators:

- 1) age (at randomization, including linear and quadratic terms)
- 2) gender (F/M)
- 3) race/ethnicity (Hispanic, Asian, Black or African American, White, Other, Unknown)
- 4) Neighborhood-level measures capturing socioeconomic status (obtained from census data linked via zip code [using most recent zip code available pre-randomization]):
  - a. median Neighborhood household income
  - b. percent Neighborhood below the federal poverty line
  - c. percent Neighborhood unemployed
- 5) Insurance status (binary indicators for the patient’s type of insurance [Medicaid, Medicare, other insurance, uninsured], using the most recent available known value pre-randomization)
- 6) Days of OUD medication treatment (in the two years pre-randomization)
- 7) Number of days with OUD documented
- 8) Comorbidity (yes/no, in the two years pre-randomization)
  - a. Alcohol use disorders
  - b. Other (non-opioid) substance use disorder
  - c. Schizophrenia and other psychotic disorders
  - d. Weighted summary score of other comorbidities (Elixhauser index, pulling out a-c above).
9. Housing instability, including homelessness (indicator for having a V or Z code in the two years pre-randomization)

Note that some of these covariates (e.g., race/ethnicity; insurance status) have some missing values; the approach to handling missing data in adjustment variables is described below in Section 8.1.

#### **5.4.2 Objective 2 Sensitivity Analysis Among “Active” Patients**

Because we have a visit-based sample, we do not know when a patient is no longer observable (e.g., switched clinics, moved, went elsewhere for medical or OUD treatment, or died), except among enrolled patients in HCSs with insurance claims (discussed in the following section). In particular, we cannot distinguish between a patient who has no acute care utilization over the follow-up period and a patient who has acute care utilization outside of the health system (that is not captured across all HCSs in our data). To address this, we plan to repeat the primary analysis among the subset of patients who are “active in the HCS”, defined as having any evidence that they are still observable (e.g., any visit (PC and non-PC), or diagnosis anywhere in the health system during follow-up). In addition, we plan to conduct a second sensitivity analysis among patients “active in PC”, defined as having a PC visit to their “assigned” trial clinic during the follow-up period.

#### **5.4.3 Objective 2 Sensitivity Analysis Among Patients Enrolled in the HCS Health Plan**

Two of the HCSs are integrated health systems that insure a subset of the patients who receive clinical care in the health system. We will examine the proportion of patients with an OUD diagnosis at baseline who are in the insured sample and who were enrolled in the health plan at the time of randomization. Descriptively, we will compare the estimated outcome rate separately within each of these two HCS in a model that accounts for enrollment as compared to the main analysis approach that does not account for enrollment (e.g., by comparing the mean number of days of acute care utilization per year enrolled vs. the mean number of days of acute care utilization per year of the 2-year HCS follow-up period).

In addition, depending on the size of the subsample, we will consider repeating the primary Obj. 2 analysis among this subsample. The offset term will be slightly modified from the primary analysis: rather than use the amount of possible follow-up from the randomization date, we will use more precise information on the number of days the patient was continuously enrolled in the health plan post-randomization during the available follow-up period (allowing gaps of up to 90 days). Although this proposed analysis is only available on a subset of the Objective 2 primary sample in the 2 HCSs, by restricting to enrolled patients and accounting for follow-up time in which the patient was enrolled (such that their outcome data is known to be observable), analyses within this sample could mitigate issues whereby outcomes of patients included in the primary Objective 2 visit-based sample may not be observable (e.g., if they left the health system or accessed acute care outside the system). Understanding differences in this analysis and HCS-level estimates for these sites will aid in interpretation of findings.

#### **5.4.4 Objective 2 Sensitivity Analysis Addressing Clinic Assignment/crossover**

We will follow a similar approach as the above Objective 1 sensitivity analysis (see Section 5.2.3 above). Specifically, if we observe that any patients assigned to a UPC clinic is ever treated in the intervention clinic at that HCS during the follow-up period, we will apply an alternate algorithm in which patients are assigned to the clinic where they have the most PC visits post-randomization.

#### **5.4.5 Objective 2 Secondary Modified Analyses Accounting for Success of Implementation**

We will conduct secondary modified analyses accounting for success of implementation following a similar approach as for Objective 1 (see Section 5.2.2 “Modified analyses accounting for success of implementation”), including (1) analyses restricted to the follow-up period in which the NCM was seeing patients (for which we will modify the offset term), and (2) analyses limited to HCS in which the clinic randomly assigned to the PROUD intervention successfully implemented the MA model. We also plan to repeat analysis (1) restricted to patients with an active PC visit post-randomization (Section 5.4.2).

#### **5.4.6 Objective 2 Sensitivity Analysis Applying Stricter Eligibility Criteria**

Our primary analysis requires just a single OUD diagnosis pre-randomization for a patient to be included in the sample, as well as just a PC visit at any time pre-randomization (up to 3 years). To account for the possibility that having only one diagnosis could reflect an error in identifying OUD and that patients with a PC visit early in the pre-randomization period may have left the clinic, we will conduct a sensitivity analysis among the sub-sample of our primary sample that restricts to patients with both  $\geq 2$  days with an OUD diagnosis during the pre-randomization period and a PC visit in the year prior to randomization.

### **5.5 Secondary Analyses of Primary Objective 2 Outcome Measure within the Objective 2 Secondary Sample**

Here we describe secondary analyses of the primary Objective 2 outcome measure within the larger secondary sample (see Section 3.3) that includes patients in the primary Objective 2 sample (i.e., the pre-randomization sample with a PC visit and OUD diagnosis pre-randomization), as well as the post-randomization sample of patients with newly recognized OUD in the trial clinics post-randomization.

#### **5.5.1 Rationale for Conducting Analyses Within a Secondary Sample**

It is expected that some of the patients who initiate treatment in PROUD intervention clinics will have been diagnosed with OUDs after randomization, potentially due to the PROUD intervention. It is also possible that patients may be newly attracted to the clinic (or to the health system entirely) potentially because of the PROUD intervention (based on the fact that at least 77% of patients treated in MA were new to the clinic after implementation). The primary analysis of Objective 2 described above would miss any impact of the PROUD intervention on both of these subsamples of patients, because they were not identified pre-randomization (because they were not previously diagnosed with OUDs or because they did not visit the clinic in the pre-randomization period). These secondary analyses within the secondary Objective 2 study sample, which includes patients seen in the trial clinics with an OUD diagnosis post-randomization only, are designed to capture these additional patients who may be affected by the PROUD intervention.

On the other hand, these secondary analyses must account for the fact that patients with newly recognized OUD in the PROUD intervention clinics post-randomization are likely to differ markedly from patients with newly recognized OUD in the UPC clinics post-randomization. Further, it is likely that these patients could differ in ways that may be associated with acute care utilization (e.g., patients could be referred for ongoing buprenorphine treatment from an ED or hospital that started treatment). To address this, analyses will adjust for covariates known or hypothesized to be associated with acute care utilization (based on prior literature), as well as secondarily for any additional covariate observed to differ across patients with newly recognized OUD post-randomization in the UPC versus PROUD intervention clinics.

### **5.5.2 Defining Covariates for the Objective 2 Secondary Sample That Includes Patients Not Seen in the Health System Pre-randomization**

Defining covariates using pre-randomization data is preferred for randomized studies, because this ensures that the intervention does not affect the covariate values. However, this is not possible for patients who were not seen in the HCS pre-randomization. For these patients we therefore plan to use the post-randomization value of time-varying covariates that is available closest to randomization. We note that using this approach means that analyses including patients new to the HCS post-randomization cannot adjust for “baseline” acute care utilization (since patients new to the HCS post-randomization do not have baseline data observed). We considered applying a multiple imputation approach to address missing baseline data among these patients; however, we did not think the missing at random (MAR) assumption was reasonable (i.e., we did not think using data from patients in the HCS pre-randomization was sufficient to impute data from patients new to the HCS). Therefore, sensitivity analyses will be applied to examine the subpopulation excluding these patients (see Section 5.5.4).

Decisions regarding the set of covariates to be included in analyses within this secondary sample (listed below) were made in conjunction with the Investigator team to determine whether individual covariates measured post-randomization are likely to be impacted by the intervention. We wanted to avoid including covariates that are likely to be impacted by the intervention (as they may be on the causal pathway). Although documentation of certain comorbidities were thought to be most likely to be impacted by the intervention, it was hypothesized that documentation of any comorbidities could be increased via the intervention due to increased care in general; insurance status was also plausibly thought to be related to intervention status (as poor OUD-related outcomes could affect insurance status).

Covariate adjustment: We plan to adjust for the following subset of covariates as in the secondary analysis within the primary Objective 2 sample (described above in Section 5.4.1):

- 1) age (at randomization, including linear and quadratic terms)
- 2) gender (F/M)
- 3) race/ethnicity (Hispanic, Asian, Black or African American, White, Other, Unknown)
- 4) Neighborhood-level measures capturing socioeconomic status (obtained from census data linked via zip code [using zip code available closest to randomization, prioritizing pre-randomization if available]):
  - a. median Neighborhood household income
  - b. percent Neighborhood below the federal poverty line
  - c. percent Neighborhood unemployed

In a sensitivity analysis, we will further adjust for additional covariates (including insurance status, comorbidities, and housing instability measures from Section 5.4.1) found to differ between individuals with newly recognized OUD post-randomization in the PROUD intervention clinics as compared to individuals with newly recognized OUD post-randomization in the UPC clinics (e.g., with a standardized mean difference of  $<0.10$ ). However, because differences in these covariates (e.g., comorbidities) could be affected by the intervention, results from this sensitivity analysis will be interpreted with caution.

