We will first conduct preliminary analyses to compare the characteristics of patients diagnosed with OUDs in PROUD intervention clinics and UPC clinics. Because individuals who were first diagnosed with OUD prior to randomization are expected to be comparable across PROUD

intervention and UPC clinics (due to the randomization), these comparisons will focus on patients who entered our analytic sample because they were first diagnosed with OUDs in the 2 years post-randomization. Preliminary analyses will seek to understand differences in demographic characteristics, comorbidity, and utilization patterns between patients not included in primary analyses of Objective 2, but diagnosed with OUDs in PROUD intervention clinics and UPC clinics after randomization, in order to identify covariates for these secondary analyses of Objective 2.

We plan to fit a similar mixed-effect Poisson regression model as in the primary Objective 2 analysis but that includes additional covariates that allow the treatment effect comparing the PROUD intervention clinics to UPC clinics to differ among patients who were newly identified as having an OUD diagnosis in the post-implementation period. Specifically, the model will be of the following form:

$$\log[E(y_{ijk})] = \alpha_0 + \alpha_1 \text{period}_{ijk} + (\beta_0 + \beta_1 * \text{period}_{ijk}) * \text{trt}_{ij} + \gamma * z_{ijk} + \theta_{ij}$$

where *period* is an indicator for the period when the patient had their first documented OUD (in the post-randomization study phase versus pre-randomization), and the other terms are defined as in the primary analysis. We will adjust for the same covariates (in *z*) as in our primary Objective 2 analysis described above, as well as any covariate found to differ between individuals diagnosed with OUDs after randomization in the PROUD intervention clinics as compared to the UPC clinics, as identified in our preliminary analyses described above.

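### SAP 5.5.2: the only numeric criterion for adding covariates in the Objective 2 secondary-sample sensitivity analysis (SMD below 0.10) points the opposite way from the stated intent

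*SAP*

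**What the plan says.** SAP 5.5.2 fixes the covariates for the main model in the Objective 2 secondary sample: "We plan to adjust for the following subset of covariates as in the secondary analysis within the primary Objective 2 sample", followed by age, gender, race/ethnicity and three neighborhood measures. No screening is involved.

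It then describes an extra analysis: "In a sensitivity analysis, we will further adjust for additional covariates (including insurance status, comorbidities, and housing instability measures from Section 5.4.1"). These covariates enter if they are "found to differ between individuals with newly recognized OUD post-randomization in the PROUD intervention clinics as compared to individuals with newly recognized OUD post-randomization"; the second group is the UPC patients. A bracketed example gives the only number: "with a standardized mean difference of" <0.10.

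The intent is stated in two other places, neither with a cut-off. SAP 5.5.1 says the analyses will adjust for predictors of acute care use, "as well as secondarily for any additional covariate observed to differ across patients with newly recognized OUD post-randomization in the UPC versus PROUD intervention clinics". Protocol 11.2.2.2 plans to adjust for the primary-analysis covariates "as well as any covariate found to differ between individuals diagnosed with OUDs after randomization in the PROUD intervention clinics as compared to the UPC" arm.

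**The concern.** A standardized mean difference (SMD) measures how far two groups are apart, so a value under 0.10 describes groups that are alike. The sentence asks for covariates that differ and illustrates this with the range in which they do not. It also omits to say that the SMD is absolute.

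The comparison concerned is not protected by randomization. SAP 3.4 restricts the primary Objective 2 sample in order to avoid identification bias. SAP 5.5.1 expects newly recognized patients to differ considerably between arms, possibly in ways tied to acute care use. SAP 5.5.3 regards unmeasured confounding as the likelier explanation of a non-zero interaction. The main secondary-sample model holds only demographics and neighborhood measures, and cannot include baseline acute care use because patients new to the health system have none recorded.

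This sensitivity analysis is therefore the one place where insurance, comorbidity and housing can enter for the whole secondary sample, new patients included. If it selects the wrong covariates, it does not answer the question it was written for.

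**Working it through.** There is no sample size, power or alpha figure to reproduce. The check sets the threshold against the wording and then illustrates it.

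**1. Direction.**
- SAP 5.5.2, wording: add covariates that differ.
- SAP 5.5.1: add covariates that differ.
- Protocol 11.2.2.2: add covariates that differ.
- SAP 5.5.2, example: add if SMD <0.10, that is, if similar.

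Three statements agree and the one number contradicts them. No other section of either document gives an SMD cut-off that could correct it.

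**2. Illustration.** For a binary covariate with prevalence p1 in PROUD and p2 in UPC:

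SMD = (p1 − p2) / √{[p1(1 − p1) + p2(1 − p2)] / 2}

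The documents give no prevalences by arm for this sample. I assume p2 = 30% and vary p1 from 20% to 45%. For p1 = 40%: 0.10 / √[(0.24 + 0.21)/2] = 0.10 / 0.474 = 0.211.

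| PROUD vs UPC | SMD (PROUD − UPC) | Absolute SMD <0.10 (literal) | Signed, PROUD − UPC <0.10 | Signed, UPC − PROUD <0.10 | Absolute SMD ≥0.10 (intended) |
|---|---|---|---|---|---|
| 30% vs 30% | 0.000 | added | added | added | not added |
| 32% vs 30% | 0.043 | added | added | added | not added |
| 34% vs 30% | 0.086 | added | added | added | not added |
| 35% vs 30% | 0.107 | not added | not added | added | added |
| 40% vs 30% | 0.211 | not added | not added | added | added |
| 45% vs 30% | 0.314 | not added | not added | added | added |
| 20% vs 30% | −0.232 | not added | added | not added | added |

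On the absolute scale the literal rule is the exact complement of the intended one. On the signed scale every near-balanced covariate enters, and an imbalanced one enters or not according to the order of subtraction, which the SAP does not state.

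**3. Reach.**
- Primary Objective 1 (SAP 5.1) and primary Objective 2 (SAP 5.3): each adjusts only for the baseline value of its outcome. Unaffected.
- Main secondary-sample model (SAP 5.5.2 and 5.5.3): fixed covariate list. Unaffected.
- SAP 5.5.4.a: full 5.4.1 list, no screen, limited to patients in the health system before randomization. Unaffected, but it leaves out patients new to the system.
- SAP 5.5.4.b: repeats several sensitivity analyses in the secondary sample; the 5.4.1 covariate-adjusted model is not among those it names.
- The sensitivity analysis in SAP 5.5.2: affected.

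**The case against.** The strongest reply is that the governing words are right and only an example is wrong. Read with SAP 5.5.1 and the protocol, nobody could doubt the intent, so harm requires a programmer to follow the bracket against the sentence around it. That is fair, and a slip of the sign is the likeliest explanation. But the example is the only number available to code from. If it is set aside, the plan has no cut-off, and what counts as differing is decided after the data are seen. The sentence needs correcting either way.

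The point also turns on one character in text extracted from a PDF. An extraction error cannot be ruled out, and the signed SAP should be checked first.

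The stakes are limited too. SAP 5.5.3 calls these analyses exploratory, and SAP 5.5.2 already promises caution for this one. That caution, however, concerns covariates the intervention may have altered, not selection of the wrong ones. The Objective 2 Table 1 shell reports insurance, housing and comorbidity by arm for the post-randomization sample, so a careful reader could notice a misapplied screen.

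Three stronger inferences are tempting and not supported:
- **That every imbalanced covariate would be lost.** This follows only on the absolute reading; on the signed reading, imbalances in one direction are kept.
- **That the analysis would reproduce the main secondary-sample estimate and look falsely robust.** Nothing shows this. The screen is applied to newly recognized patients, but the model is fitted to the whole secondary sample with a period interaction, so covariates balanced in one part can still move the estimates.
- **That these confounders are handled nowhere else, or that all should be adjusted for without a screen.** SAP 5.5.4.a handles them for patients already in the health system. SAP 5.5.2 explains why unscreened adjustment was avoided: measured after randomization, such covariates may lie on the causal pathway.

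**Conclusion.** The concern holds in limited form. The only numeric criterion in SAP 5.5.2 for adding covariates contradicts its own sentence, SAP 5.5.1 and Protocol 11.2.2.2. Followed literally on the absolute scale, it selects near-balanced covariates and omits imbalanced ones; as a signed difference, it makes selection depend on an unstated convention.

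The size cannot be put as an effect on the estimate, because the documents give no covariate distributions by arm for this sample. The worked prevalences are assumptions that show direction only. The consequence is confined to one exploratory sensitivity analysis, and matters most for patients new to the health system, whom SAP 5.5.4.a does not cover. It should not be read as a defect in the trial's main conclusions on either objective. The verdict assumes that the printed symbol is as extracted and that the code follows the number rather than the words.

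**What to change.** After checking the symbol in the signed SAP, replace the bracketed example in 5.5.2 with a fixed rule: an absolute standardized mean difference of 0.10 or more, taking the largest level-specific value for covariates with several levels, such as insurance type. Delete the abbreviation that makes the cut-off a mere example, so that the rule is set in advance. Confirm that the analysis code uses the same direction and the absolute value. Keep the screen and the existing caution about covariates the intervention may affect.

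The cost is a few words in the SAP and one line of code to check. No new data are needed, and no other analysis changes.

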### **5.5.3 Primary Objective 2 Outcome Analysis within the Secondary Sample**

We plan to fit a similar mixed-effect Poisson regression model as in the primary Objective 2 analysis but that (1) includes additional covariates and (2) that allows the treatment effect comparing the PROUD intervention clinics to UPC clinics to differ among patients with newly

recognized OUD in the clinics post-randomization vs. those with visits to the trial clinics and OUD documented pre-randomization. Specifically, the model will be of the following form:

$$\log[E(y_{ijk})] = \log(\text{days}_i) + \alpha_0 + \alpha_1 \text{period}_{ijk} + (\beta_0 + \beta_1 * \text{period}_{ijk}) * \text{trt}_{ij} + \gamma * z_{ijk} + \theta_{ij}$$

where *period* is an indicator for the period when the patient was first recognized with OUD in the trial clinics (i.e., whether the patient is in the post-randomization sample or pre-randomization sample; see Section 3.3), and the other terms are defined as in the primary analysis, except for the covariate vector (*z*), which includes the set of covariates listed above in Section 5.5.2.

We will evaluate our secondary Objective 2 hypothesis by testing the composite null hypothesis  $H_0: \beta_0 = \beta_1 = 0$  versus the alternative hypothesis that at least one of  $\beta_0$  or  $\beta_1$  is non-zero by conducting a likelihood ratio test. Additionally, we will estimate the treatment effect separately among patients identified in the pre-randomization period ( $\beta_0$ ) and patients identified in the post-randomization period ( $\beta_0 + \beta_1$ ). The coefficient  $\beta_1$  is the difference in the treatment effect comparing patients identified post-randomization to those identified in the pre-randomization period. This could either reflect a true difference in the treatment effect, or, more likely, it could reflect unmeasured confounders (not included in *z*) that differ between patients newly recognized with OUD post-randomization in the intervention versus UPC trial clinics. We do not have a specific hypothesis regarding  $\beta_1$  because new patients may be attracted to the clinic to receive the PROUD intervention, as seen in [name], and these patients may be sicker (or healthier) than patients identified pre-randomization, or more motivated for treatment, which could increase (or decrease) acute care utilization during the period after randomization. We are not powered to test for the difference in intervention effects between these two groups ( $\beta_1$ ); rather, the analyses proposed here are exploratory analyses that will generate hypotheses for testing in future studies.

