### **2.4 Follow-up or “Post-randomization” Period**

Unless otherwise specified, the follow-up period is defined as the period from study day 1 to 2 years after the randomization date (or 1.5 years for one health system that randomized 6 months late). For simplicity, throughout the SAP this follow-up (“post-randomization”) period is referred to as 2 years.

[figure not shown]

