#### 3.4 Objective 2 Secondary Study Sample

The Objective 2 primary sample as defined in the preceding section, which restricts analyses to patients seen in PROUD trial clinics with documented OUD pre-randomization, was selected for primary analyses to avoid the potential for *identification bias* (type of selection bias that can occur when the analytic sample is defined using post-randomization data). However, an important limitation of analyses within the Objective 2 primary sample is that they miss any impact of the PROUD intervention among patients with a new OUD diagnosis post-randomization, including patients who initiate treatment in PROUD intervention clinics who are diagnosed with OUDs after randomization, and patients who are newly attracted to the clinic specifically because of the PROUD intervention. To address this limitation, secondary analyses are conducted in a broader sample that includes patients new to the PROUD trial clinics or with newly recognized OUDs post-randomization (see Figure Shell 1, Objective 2 paper, Section 10.2).

Specifically, the effectiveness (Objective 2) secondary study sample is defined as the subset of patients from the main trial sample who had a documented OUD diagnosis during either the pre-

randomization or follow-up periods and who were age  $\geq 16$  as of the start of the baseline period. Clinic assignment for the Objective 2 secondary sample will be the same as above.

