#### **4.2 Definition of Objective 2 Effectiveness Outcome Measure (Powered Secondary Outcome)**

The primary effectiveness (Objective 2) endpoint is a person-level count measure of the number of days of acute care utilization in the follow-up period, among patients with an OUD diagnosis pre-randomization. This measure includes visits to urgent care clinics or emergency departments (EDs), as well as days hospitalized. Acute care utilization will be determined from the EMR and insurance claims data when available.

For hospitalizations, the number of inpatient days will be the number of days from admission to discharge, inclusive. For urgent care or ED (referred to collectively as “emergency care”), each unique date with a visit to an urgent care or ED will be counted as 1 day (even if the patient stays overnight), except in the uncommon event that an ED visit spanned 3 or more days ( $< 0.5\%$  of ED records collected in Data Pull 4, including both randomized and non-recruited UPC clinics), in which case the encounter will be classified as a hospitalization (as patients may be boarded in an ED until a hospital bed becomes available and some are subsequently discharged from the ED if no hospital bed ever became available). If a patient is admitted from urgent care or an ED, the ED or urgent care day is not (double) counted when counting the number of days of acute care.

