Because one of the HCSs was randomized at a later date than the others, not all HCSs have the same amount of follow-up time. To account for this difference, we will include in the model an offset term for the number of days of potential follow-up time (e.g., 2 years for 5 of the HCSs and 1.5 years for the 6th HCS); in the above model,  $\log(\text{days}_j)$  denotes the offset term where  $\text{days}_j$  denotes the days of follow up in HCS  $j$ .

We will evaluate our primary Objective 2 hypothesis by testing the null hypothesis  $H_0: \beta = 0$  versus the two-sided alternative hypothesis that  $\beta$  is non-zero with a type 1 error rate of 0.05. In cluster-randomized trials with a small number of clusters, a small-sample correction is often necessary to obtain correct type 1 error rates. Although small-sample degree of freedom (DF) correction methods have been evaluated for continuous and binary outcomes under generalized linear mixed-effect models (GLMMs), there has not been prior guidance of which approach to use in our setting with a count outcome and covariate adjustment. Given this lack of knowledge, members of the PROUD statistical team are conducting simulations to evaluate alternate small-sample DF methods in this setting. Our results so far suggest that the optimal choice of testing procedure varies depending on the data-generating scenario in terms of the intraclass correlation

coefficient (ICC), number of clusters, and sample size within a cluster; however, using the likelihood ratio test with the Between-Within (BW) DF correction method (also referred to as “inner-outer” approach) appears to perform generally well in the scenario that aligned most closely with PROUD Phase 1 data used in the power simulation (see Appendix C).

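### In the exploratory secondary-sample model for Objective 2, patients who first reach the health system after randomization are given its full follow-up as exposure, so their acute-care rates are understated

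*SAP*

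**What the plan says.** The Objective 2 outcome (SAP 4.2) is "the number of days of acute care utilization in the follow-up period", and SAP 2.4 states that "the follow-up period is defined as the period from study day 1 to 2 years after the randomization date", or 1.5 years at the HCS that randomized late. For the primary model, SAP 5.3 says "we will include in the model an offset term for the number of days of potential follow-up time". The quantity inside that offset "denotes the days of follow up in HCS" j, so it takes one value per HCS.

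SAP 3.4 explains that "secondary analyses are conducted in a broader sample that includes patients new to the PROUD trial clinics or with newly recognized OUDs post-randomization". The footnotes to the Objective 2 Table 1 shell confirm that this includes patients new to the HCS after randomization. SAP 5.5.3 models this sample with separate treatment effects for patients identified before randomization (β0) and after it (β0 + β1). On everything else it says "the other terms are defined as in the primary analysis, except for the covariate vector". Its displayed equation gives the offset the subscript i where 5.3 has j, but i indexes clinics, so neither form is patient-specific.

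Under SAP 8.1, an event with no record is taken not to have happened. SAP 5.5.2 does discuss new-to-HCS patients, but only as a covariate problem: "patients new to the HCS post-randomization do not have baseline data observed". SAP 5.4.2 discusses observability only as patients leaving.

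**The concern.** A Poisson model with an offset estimates a rate only if the count and the exposure cover the same time at risk of being observed. For a patient whose first recorded HCS contact is at month 20, the model uses 24 months of exposure. The first 20 contain no recorded acute care by construction, since any recorded visit would itself have been the first contact.

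The SAP allows for late entry elsewhere. Its 6-month retention measure (Table 2) excludes patients whose only eligible visit, or whose treatment start, falls in the last six months. It makes no such allowance for acute care.

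At stake are β0 + β1, the omnibus test of β0 = β1 = 0, and the per-year rates for the post-randomization sample in Table Shell 5. SAP 5.5.1 expects newly recognised patients to differ by arm and expects the intervention possibly to draw in people from outside the HCS. An arm difference in entry is therefore plausible. The SAP already warns that β1 may reflect unmeasured confounding, but a reader would not know that part of it could be an exposure artefact that recorded dates can reduce.

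**Working it through.** **The plan's own rate.** SAP 6.2.1 takes 4.0 acute care visits per patient over two years at 2.04 days each: 4.0 × 2.04 = 8.16 days, and ln(8.16) = 2.099, stated as 2.1. The SAP gives no rate, sample size or power for the secondary-sample model, so 8.16 serves only as illustration.

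**One new-to-HCS patient.** Let F be the months of follow-up and e the month of first HCS contact. With a constant true rate and no capture before e, the apparent rate divided by the true rate is (F − e)/F.

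- F = 24, e = 6: 18/24 = 75% (6.12 of 8.16 days counted)
- F = 24, e = 12: 12/24 = 50% (4.08 days)
- F = 24, e = 18: 6/24 = 25% (2.04 days)
- F = 18 (the late HCS), e = 6: 12/18 = 67%; e = 12: 6/18 = 33%

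**Arm comparison in the post-randomization sample.** Let f be the share of an arm's patients who are new to the HCS and e their mean entry month. With the same true rate for everyone, the arm's apparent rate divided by its true rate is 1 − f × e/F. With no treatment effect, the spurious rate ratio (RR) is the intervention value over the UPC value. This ignores covariates and clinic random intercepts. All f and e below are assumptions, with F = 24.

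| Share new to HCS, intervention / UPC | Mean entry month, intervention / UPC | Calculation | Spurious RR |
|---|---|---|---|
| 40% / 20% | 12 / 12 | 0.80/0.90 | 0.89 |
| 50% / 25% | 12 / 12 | 0.75/0.875 | 0.86 |
| 60% / 20% | 12 / 12 | 0.70/0.90 | 0.78 |
| 50% / 50% | 12 / 12 | 0.75/0.75 | 1.00 |
| 50% / 50% | 15 / 12 | 0.6875/0.75 | 0.92 |
| 50% / 50% | 9 / 12 | 0.8125/0.75 | 1.08 |
| 0% / 0% | not applicable | 1/1 | 1.00 |

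The Massachusetts figure in 5.5.1, at least 77%, is the share of treated patients new to the clinic, not to the health system, so it cannot stand in for f.

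**Do the planned sensitivity analyses deal with it?**

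- 5.5.4.a restricts to patients in the HCS before randomization. This removes the exposure error, but by dropping the affected patients.
- The active-patient restrictions (5.4.2, applied through 5.5.4.b) leave the offset unchanged.
- The enrolled-patient analysis (5.4.3) uses patient-level enrolled days, but covers two HCSs and is framed around patients enrolled at randomization.
- The implementation-period analysis (5.4.5) moves the offset by HCS, not by patient.

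None keeps the late entrants and gives them their own exposure.

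**The case against.** The strongest reply has four parts.

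First, most late-recognised patients may have no exposure error. A reader might infer that anyone recognised with OUD after randomization is wrongly offset. The documents do not support that. Patients already in the HCS are counted over the full follow-up and offset by the same period. Including care that preceded recognition, such as the route named in 5.5.1 ("patients could be referred for ongoing buprenorphine treatment from an ED or hospital that started treatment"), is a choice of time zero, not a wrong denominator. This part stands in full.

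Second, a reader might infer that the bias favours the intervention. The shares and entry times are assumed, equal patterns give 1.00, and plausible differences fall on either side. This stands too: only the potential for a difference between arms is supported.

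Third, time before first contact may not be wholly unobserved. Acute care inside the HCS would have been recorded from study day 1, and a visit-based sample has no date at which observability begins. This limits the size: where earlier care would have come to the HCS, the shortfall is smaller than (F − e)/F implies. It does not justify assuming full capture for every new patient.

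Fourth, the SAP calls the analysis exploratory, labels Table Shell 5 observational, and plans 5.5.4.a. That lowers the priority. But 5.5.4.a was planned because of missing baseline data, and it drops the patients attracted from outside the HCS, one of the groups the wider sample was meant to capture.

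**Conclusion.** The point holds for patients first seen in the HCS after randomization, in the 5.5.3 model and in the analyses that repeat it with these patients included. Their rate is understated to 75%, 50% or 25% of the true value for entry at month 6, 12 or 18 of 24, given a constant rate and no capture before entry. The effect on β0 + β1 and the omnibus test is conditional: it is nil if the share and timing of new-to-HCS patients match across arms, and about 0.89 under assumed shares of 40% and 20% with mid-follow-up entry. The documents give neither share nor timing, so no size or direction can be stated as fact.

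It would be wrong to extend the point to the main Objective 2 result. The primary sample (SAP 3.3) requires an eligible visit and an OUD diagnosis before randomization, so late entry cannot arise there.

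**What to change.** In SAP 5.5.3, in the 5.5.4.b analyses that retain these patients, and in Table Shell 5:

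1. For patients new to the HCS after randomization, start both the acute-care count and the offset at first observed HCS contact. Use the log of patient-specific days from that contact to the end of follow-up.
2. Keep randomization as the origin for everyone already in the HCS.
3. Report entry time and the new-to-HCS share by arm.
4. Present 5.5.4.a alongside, as the estimate free of this exposure error.

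The cost is SAP wording and modest programming, since the visit and diagnosis dates are already extracted (Protocol 5.4.1, Table 4). There are two downsides. Late entrants contribute less person-time. The first contact may itself be an ED visit or admission, which would inflate the rate from that point, so results should also be shown with that index encounter excluded.

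Starting the clock at OUD recognition for patients already in the HCS should be at most an additional sensitivity analysis. The intervention is expected to change recognition, and that origin would discard time that was properly observed.
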